This is why *in vivo* studies of FC bioavailability are becoming more common and necessary, as this allows us to show beyond the detailed characterization of the compounds present in the various extracts. In the case of hibiscus, there are studies that have shown, both in hypercholesterolemic animals and in animals fed a high-fat diet, how the intake of the compounds present influences the decrease in markers of oxidative stress and in expression of satiety hormones (Moyano et al., 2016; Sayago-Ayerdi et al., 2014). On the other hand, it has been until the characterization of hibiscus calyx extracts from improved varieties and the *in vitro* predigestion of these calyxes, that it has been possible to establish a wide percentage of compounds present in Hibiscus capable of being bioaccessible (Sayago-Ayerdi et al., 2021). In this analysis, 49 compounds were obtained, of which five are organic acids such as Hibiscus, which is found in high concentration in the characterization but, after *in vitro* digestion, less than half remains, indicating that it may be bioavailable; Something similar happens with hydroxycitric acid, but this bioaccessibility is even more marked in the case of flavonoids such as quercetin-3-sambubioside or kaempferol-3-glucosides, which are not even

detected after *in vitro* digestion. Likewise, anthocyanins such as delphinidin-3-sambubioside contained in hibiscus are almost totally bioaccessible after digestion (Sayago-Ayerdi et al., 2021). This indicates the potential bioaccessibility of the phenolic compounds present in hibiscus calyxes that are the product of decoction.

BIOAVAILABILITY OF BIOACTIVE COMPOUNDS BY CLINICAL TRIALS

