Metabolite identification in plasma and urine samples was carried out in the same system performed by the following methodology according to Mateos et al., (2016), using 30 μl of plasma and 5 μl of urine were injected separately under isocratic conditions in a high-performance liquid chromatograph (HPLC-DAD-MS) coupled to a mass spectrometer (Agilent 1260). Water (Phase A) and acetonitrile (Phase B) acidified with 0.1% formic acid at a flow rate of 0.4 ml/min were used as mobile phase. The phase was initially programmed with 95% of solvent A and then 5% of B. The elution program was increased to 10% of solvent B in 10 min and 60% of solvent B in 5 min, which was maintained for 2 min. The initial conditions (5% of solvent B) were recovered 1 min and maintained for 2 min. The conditions for the mass chromatograph were as follows. Identification of CF and organic acids was carried out using an Agilent 1260 series HPLC system (Agilent Technologies, Santa Clara, CA, USA) equipped with a UV-Vis diode array detector (DAD). Samples were injected onto a Poroshell 120 EC-C18 column (4.6 mm \times 150 mm, particle size 2.7 μm) (Agilent Technologies). Detection will be performed in a specific nm range. For MS analysis, an Agilent Quadrupole LC / MS 6120 equipped with an electrospray ionization interface in negative ionization mode will be used with specific conditions of: drying gas flow; nebulizer pressure; gas drying temperature; and capillary voltage. Data analysis was performed using OpenLab CDS ChemStation Edition software (Agilent Technologies, Santa Clara, CA, USA). Characterization was based on retention time and mass spectrometry data. Compounds were first detected using a single MS scan in the specific range (m/z), followed by a targeted search based on peaks showing major signals in the UV-Vis chromatograms. Due to the lack of standards for phase II metabolites, tentative quantification of calibration curves corresponding to phenolic compounds and precursor organic acids was performed. The urine results will be normalized with the volume excreted in each interval studied.

Enzyme inhibition.

In vitro gastrointestinal digestion of the beverages.

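### Only negative-ion mass spectrometry is described, so anthocyanins may be poorly detected and a non-detect could be misread as lack of bioavailability

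*Combined protocol and SAP*

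**What the plan says.** The relevant text is in the section on characterization and quantification by HPLC-DAD-MS.

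- **Ionization.** The MS unit is "equipped with an electrospray ionization interface in negative ionization mode will be used with specific conditions of" drying gas flow, nebulizer pressure, drying temperature and capillary voltage, none of which is given a value. No other polarity is mentioned in the document.
- **Mobile phase.** Water and acetonitrile, "acidified with 0.1% formic acid at a flow rate of 0.4 ml/min were used as mobile phase".
- **Second detector.** The same system has a UV-Vis diode-array detector. Of its range the text says only: "Detection will be performed in a specific nm range".
- **Order of detection.** "Compounds were first detected using a single MS scan in the specific range (m/z), followed by a targeted search" that is guided by the larger UV-Vis peaks.
- **Identification.** "Characterization was based on retention time and mass spectrometry data".
- **Quantification.** Phase II metabolites lack standards, so "tentative quantification of calibration curves corresponding to phenolic compounds and precursor organic acids was performed". No detection limit, quantification limit or recovery is given, and no anthocyanin standard is named.

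On the compounds themselves, the section on functional properties classes anthocyanins as phenolic compounds, lists them among the active components and credits them with ACE inhibition. It also reports from in vitro work that "anthocyanins such as delphinidin-3-sambubioside contained in hibiscus are almost totally bioaccessible after digestion". Table 2.1 lists the delphinidin and cyanidin glycosides. Specific objective 3 covers organic acids and phenolic compounds in plasma and urine. Objective 4 takes forward the metabolites found to be bioavailable in plasma.

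**The concern.** The assay is described in one polarity, and that polarity is not the one generally favoured for a compound class that the rationale puts near its centre. Negative mode suits organic acids, phenolic acids and their conjugates. Anthocyanins in an acidified eluent carry a positive charge and would usually be looked for in positive mode.

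The stake is how a negative result would be interpreted. If anthocyanins do not appear in plasma, the reader cannot tell whether they were not absorbed or whether the instrument responded weakly to them. The plan has no detection limit and no rule that separates the two. Because objective 4 works only on what objective 3 identifies, a missed anthocyanin would also leave the immunomodulatory assessment.

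**Working it through.** The plan states no figure to reproduce: it gives no detection limit, no anthocyanin content for the 60 ml drink and no expected plasma or urine level. The check is therefore mainly textual, followed by an illustration on assumed inputs.

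**1. Are anthocyanins in scope?** Objective 3 covers phenolic compounds as a class, and the functional-properties section places anthocyanins in that class. They are in scope, although not named as a separate analyte.

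**2. Is there another route to detecting them?** The diode array does not depend on ionization polarity, so it is a real second route. Three features of the text limit it:
- the first detection step is an MS scan;
- the follow-up search starts from major UV-Vis signals, which a trace plasma analyte may not give;
- characterization uses MS data as well as retention time, so a UV-Vis peak alone does not meet the stated basis for identification.

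The wavelength range is not given, so it is also unknown whether a wavelength suited to anthocyanins is recorded.

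**3. Is the outcome protected by a reporting rule?** No limit of detection and no rule for values below it is stated.

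**4. Illustration of what a sensitivity loss could do.** From the protocol: seven post-drink blood samples at 0.5, 1, 1.5, 2, 3, 4 and 6 h. Everything else is assumed: a one-compartment curve C(t) ∝ exp(−ke·t) − exp(−ka·t), half-life 2 h (ke = ln 2 / 2 = 0.347 per h), ka = 1 or 2 per h, and R = true peak divided by the positive-mode detection limit. With an f-fold loss of sensitivity, a sample is detectable when R × C(t)/Cmax ÷ f ≥ 1.

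C(t)/Cmax at the seven times:
- ka = 1: 0.629, 0.911, 0.997, 0.979, 0.816, 0.622, 0.329
- ka = 2: 0.826, 0.999, 0.952, 0.841, 0.613, 0.436, 0.218

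Detectable samples out of 7 (ka = 1 / ka = 2):

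| R | no loss | 3-fold loss | 10-fold loss |
|---|---|---|---|
| 5 | 7 / 7 | 6 / 5 | 0 / 0 |
| 10 | 7 / 7 | 7 / 6 | 0 / 0 |
| 11 | 7 / 7 | 7 / 6 | 3 / 2 |
| 15 | 7 / 7 | 7 / 7 | 4 / 4 |
| 30 | 7 / 7 | 7 / 7 | 6 / 6 |

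The zero at R = 10 is a knife edge. A 10-fold loss puts the theoretical peak exactly at the limit (10 ÷ 10 = 1), and no sampling time falls exactly on the peak. At R = 11 the same loss leaves 2 to 3 samples. The table shows only that the consequence can run from nothing to complete loss, depending on quantities that the plan does not give.

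**The case against.** The strongest case against has four parts.

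- **The premise comes from outside the documents.** Nothing in them says that negative mode is insensitive to anthocyanins. This stands as to size: the loss is unknown. The direction needs only the cationic form of anthocyanins in acid, and the acid is in the protocol.
- **The diode array is a second detector, and urine is a second matrix.** This stands in part. The diode array may well show anthocyanins in the beverage. Urine is sampled to 24 h and could show what plasma does not. Neither removes the reliance on MS data for characterization, and objective 4 is tied to plasma.
- **Negative mode fits much of the target.** The background stresses metabolites formed after absorption, and the method anticipates phase II metabolites. This stands, and is why negative mode should be kept.
- **The section follows a cited method and is visibly a summary.** Missing wavelength and m/z ranges may be found in that source. This is fair, but the polarity is stated explicitly, so the point goes beyond missing detail.

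A reader might go further and infer that anthocyanins cannot be measured at all here, or that the trial will report them as not bioavailable. The documents support neither. A weaker response is not the absence of one, and the plan contains no rule that equates a non-detect with lack of bioavailability. Nor do the sample counts above predict anything about this assay, since every input apart from the sampling times is assumed.

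**Conclusion.** The concern holds in a limited form. As described, the plan does not show that anthocyanins can be adequately detected in plasma and urine, and the one polarity named is generally the less favourable one for them in an acidified eluent. A non-detect would be ambiguous and could carry through from objective 3 to objective 4.

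The size cannot be stated: on the assumed curve it runs from no samples lost to all seven. The conclusion rests on one outside premise, that anthocyanins are cations in acid and generally respond better in positive mode, and on the text being a complete account of the polarities used. It concerns the anthocyanin subclass only. Nothing in the documents suggests an effect on organic acids, phenolic acids or other conjugates, and IL-6, TNF-α, glucose and insulin are measured by separate means. It is worth acting on because the remedy is cheap and bears directly on the trial's bioavailability question.

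**What to change.** 1. Add positive-ion acquisition for the anthocyanins in Table 2.1 and their conjugates, by polarity switching or by a second injection of the same or remaining extract. Apply it equally to hibiscus and placebo samples. Keep negative mode for organic acids, phenolic acids and other conjugates.
2. State the diode-array wavelength range, the m/z range, and the detection limit for anthocyanins in plasma and in urine.
3. Where positive-mode data cannot be obtained, report anthocyanins below the stated limit as *not detected by this method*, not as *not bioavailable*, and carry that wording into objective 4.

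**Cost.** Polarity switching gives slightly less scan time per ion; a second injection adds run time. The plasma extract is made up to 150 µl and 30 µl is injected, so nominally 150 − 30 = 120 µl remains before losses in centrifuging and filtering. Parts of the method are in the past tense, so acquisition may already be complete. In that case step 1 depends on remaining extract or on the aliquots stored at −20 °C, and step 3 applies regardless.

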Samples will be subjected to an in vitro digestion model adapted from the methodology by Blancas-Benitez et al., (2018). First, the samples will be subjected to an enzymatic hydrolysis process with pepsin at a temperature of 37°C for 1 h (step 1); the phenolic compounds (FC) released in the supernatant at this stage are considered as the FC present in the gastric fraction (GasF). Subsequently, the samples are hydrolyzed with pancreatin 5 mg/ml, P-1750, Sigma Aldrich) and α -amylase (120 mg/ml, A-6255, Sigma Aldrich) (step 2). The CF released at this stage of digestion is considered the CF present in the intestinal fraction (IntF).

α -amylase activity.

The products obtained from the various stages of sample digestion will be used to determine the α -amylase enzyme activity (U/mL) using the kinetic method proposed in the specifications of the amylase activity assay kit (Sigma-Aldrich #MAK009), which consists of taking an aliquot of 50 μ L of the various samples and depositing them in a 96-well plate, then mixed with 100 μ L of master solution, previously prepared with 50 μ L of amylase assay buffer and 50 μ L of α -amylase substrate mixture, then incubated at 25°C and at minute 3, the absorbance at 405 nm is measured to obtain the initial time (T-initial) using the Synergy HT microplate reader (Biotek Instruments, Inc. , USA), readings will be taken every 5 min until the values of the samples approach that obtained at the highest concentration of the standard (20 nM/well) giving rise to the T-final. A calibration curve will be performed with Nitrophenol at concentrations of 4, 8, 12, 16 and 20 nM/well. One enzyme unit is the amount of amylase that cleaves ethylidene-pNP-G7 to generate 1 mM p-Nitrophenol per min. The enzyme activity will be expressed as percentage inhibition (I%) and determined with the equation (Eq 6.1):

$$I\% = \frac{(B \times \text{Factor de dilución})}{\text{Tiempo de reacción} \times V} \quad \text{Ec 4.1}$$

Where:

B refers to the amount of Nitrophenol generated, reaction time is the T-final minus T-initial in minutes and V denotes the volume of sample added to the well (μ L).

α -glucosidase activity.

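### The α-amylase formula labelled percentage inhibition (Ec 4.1) computes activity and falls as inhibition rises; the α-glucosidase formula (Ec 4.2) also stops at activity

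*Combined protocol and SAP*

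**What the plan says.** In the Combined protocol and SAP, specific objective 5 is to evaluate the inhibition of α-amylase and α-glucosidase by the beverages, with placebo and treatment both named. The general objective includes the same inhibition, and Expected Results offers it as one mechanism for lower glucose and insulin.

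The section on α-amylase activity begins by saying that the assay determines "enzyme activity (U/mL) using the kinetic method proposed in the specifications of the amylase activity assay kit". It then states: "The enzyme activity will be expressed as percentage inhibition (I%) and determined with the equation". The equation is cited as Eq 6.1 and printed as Ec 4.1:

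I% = (B × dilution factor) / (reaction time × V)

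The product and time terms are defined beneath it: "B refers to the amount of Nitrophenol generated, reaction time is the T-final minus T-initial in minutes". The remaining term, in µL, has its own definition: "V denotes the volume of sample added to the well". The same section says "One enzyme unit is the amount of amylase that cleaves ethylidene-pNP-G7 to generate 1 mM p-Nitrophenol per min" and "A calibration curve will be performed with Nitrophenol at concentrations of 4, 8, 12, 16 and 20 nM/well".

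The section on α-glucosidase activity opens by announcing an evaluation of inhibition. It ends with Ec 4.2 (cited as Eq 6.2), which is (final − initial absorbance) / (calibrator − water absorbance) × 250, in unt/L. Neither section, nor the Statistical Analysis section, describes an uninhibited reference or a step from activity to inhibition.

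**The concern.** An inhibition percentage compares a sample with an uninhibited reference and rises as the enzyme is suppressed. Ec 4.1 has no reference and its numerator is reaction product, so suppressing the enzyme lowers the result. If the label is followed, the beverage with the stronger inhibitory effect is reported with the lower I%, and the conclusion on objective 5 is reversed for amylase. For α-glucosidase the direction is not mislabelled, but the planned calculation ends before any inhibition measure is reached. The units attached to Ec 4.1 also disagree with one another, so an absolute activity value could not be interpreted even after relabelling.

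**Working it through.** The plan gives no numerical result for either assay, so there is no figure to reproduce. The check is of what the equations return.

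**Inputs from the documents:** sample volume 50 µL; master solution 100 µL; top standard 20 nM/well; Ec 4.1 and Ec 4.2 with their definitions; and the read rule "readings will be taken every 5 min until the values of the samples approach that obtained at the highest concentration of the standard".

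**Assumptions for illustration:** an uninhibited well reaches the top standard at 5 min, and the dilution factor D is 1, 10 or 100 (the documents give none). The direction of the result depends on neither.

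**1. Dimension.** Product × D / (minutes × µL) is product per minute per microlitre. That is an activity, not a percentage.

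**2. Direction at a fixed read time.** Let A_ref be the value in an uninhibited well and q the true inhibited fraction. Product falls to B × (1 − q), so Ec 4.1 returns A_ref × (1 − q). For D = 1, A_ref = 20 × 1 / (5 × 50) = 0.08.

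| True inhibition | Ec 4.1, D = 1 | D = 10 | D = 100 | 100 × (A_ref − A_sample)/A_ref |
|---|---|---|---|---|
| 0% | 0.08 | 0.8 | 8 | 0 |
| 50% | 0.04 | 0.4 | 4 | 50 |
| 100% | 0 | 0 | 0 | 100 |

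**3. Direction under the plan's read rule.** If each well is read until it nears the top standard, B stays at 20 and time lengthens to 5/(1 − q) min. For q = 0, 50 and 75% the times are 5, 10 and 20 min. Ec 4.1 (D = 1) then gives 20/(5 × 50) = 0.08, 20/(10 × 50) = 0.04 and 20/(20 × 50) = 0.02. It falls again.

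**4. Ec 4.2.** Assume calibrator minus water absorbance is 0.9 and the uninhibited change is also 0.9. Inhibition of 0, 25, 50, 75 and 100% gives 250, 187.5, 125, 62.5 and 0 unt/L. This is correct as activity. The reference-based formula would turn these values into 0, 25, 50, 75 and 100%, but the plan does not state that step.

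**5. Units of Ec 4.1.** Take the same uninhibited well at D = 1, with 0.05 mL of sample. If 20 nM/well means 20 nmol, the rate is 20/5 = 4 nmol/min.

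- Unit taken as 1 µmol/min: 4/1,000/0.05 = 0.08 U/mL.
- Unit taken as 1 mmol/min: 4/1,000,000/0.05 = 0.00008 U/mL.
- Unit taken as a 1 mM rise per minute in the 150 µL well (50 + 100), which is 150 nmol: 4/150/0.05 = 0.53 U/mL.
- Standard and unit both read as concentrations in that well: 20 nM in 150 µL is 0.003 nmol, and 0.003/5/150/0.05 = 0.00008 U/mL.

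The spread is 0.533/0.00008, about 6,700-fold. It cancels in a ratio-based I%.

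**6. Where the enzyme is present.** The digestion section says of the gastric step that "the samples will be subjected to an enzymatic hydrolysis process with pepsin". Pancreatin and α-amylase enter only in step 2. A low value in the gastric fraction may therefore mean absent enzyme rather than inhibition. No α-glucosidase source is named in the digestion or assay sections.

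**The case against.** The strongest reply is that this is a labelling slip. The section heading, the U/mL statement, the unit definition and the definitions under the equation all describe activity; only the I% phrase is wrong, and no reported figure is miscalculated. Objective 5 does not demand a percentage, and lower activity with hibiscus than with placebo in the same intestinal fraction would be evidence of relative inhibition. Both assays defer to kit specifications that may define controls.

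Much of this stands as a limit. The activity data remain usable once relabelled, and the claim is only that no reference or conversion is described in these documents. It does not remove the point: the label is an explicit reporting rule, it runs in the wrong direction, and nothing corrects it. The plan also does not state the placebo contrast as its measure of inhibition.

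A second reply is that the unit spread comes from extreme readings, since B is called an amount and the standards are given per well. Reading nM/well only as an amount still leaves 0.53 against 0.00008 U/mL, because the ambiguity lies in the 1 mM unit definition. It is right, though, that the units do not affect a ratio.

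A third reply concerns the remedy, and it holds. A placebo reference sets placebo inhibition to zero by construction, although objective 5 lists placebo among the beverages evaluated. For α-glucosidase, a reference activity near zero would make the percentage unstable or undefined.

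**Conclusion.** The concern holds. Ec 4.1 is an activity formula labelled as percentage inhibition. Wherever amylase is present it returns A_ref × (1 − q), so it is highest with no inhibition and zero with complete inhibition. That conclusion needs no assumed value; the tabulated numbers do. Ec 4.2 is correctly labelled but stops short of inhibition. The unit definitions leave absolute amylase activity uncertain by up to about 6,700-fold across the readings shown. The effect is confined to the in vitro objective and the mechanism drawn from it; the glucose, insulin, cytokine and bioavailability outcomes are untouched. It should be fixed before the assays are reported.

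**What to change.** - Relabel Ec 4.1 as α-amylase activity. Reconcile U/mL, nM/well and the 1 mM per minute unit definition before any activity value is reported.
- Keep Ec 4.2 as α-glucosidase activity and check its own 1 mM unit definition in the same way.
- For both enzymes, state I% = 100 × (A_ref − A_sample)/A_ref, with reference and sample from the same plate and the same digestion fraction.
- Name the reference. Use placebo if the claim is inhibition relative to placebo. Use a no-beverage digestion blank if the claim is absolute inhibition, including any inhibition by placebo itself.
- Make no inhibition claim from a fraction in which the target enzyme has not been shown to be present. This covers amylase in the gastric fraction, and α-glucosidase until its source is stated.

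With placebo as the reference, the cost is text and a unit check, with no extra wells. Absolute inhibition adds one no-beverage digestion blank and a few wells per plate, and must be planned before the assays are run. If no α-glucosidase is present in the digests, the formula alone will not rescue that assay, and the documents do not allow the extra work to be costed. There is no participant burden.
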